## LIST OF ABBREVIATIONS

Abbreviation	Definition
(e)CRF	(electronic) Case Report Form
AE	Adverse Event
AESI	Adverse Event of Special Interest
APR	Annual Progress Report
ASR	Annual Safety Report
AR	Adverse Reaction
CA	Competent Authority
CI	Coordinating Investigator
CIOMS	Council for International Organizations of Medical Sciences
CM	Concomitant Medication
CSR	Clinical Study Report
CTP	Clinical Trial Protocol
DMP	Data Management Plan
DPA	Data Processing Annex
DTA	Data Transfer Agreement
DSMB	Data Safety Monitoring Board
DSUR	Development Safety Update Report
EC	Ethics Committee
EU	European Union
ECG	Electrocardiogram
EoT	End of Trial
FPFV	First Patient First Visit
GCP	Good Clinical Practice (latest version of ICH E6)
GDPR	General Data Protection Regulation
IB	Investigator's Brochure
ICF	Informed Consent Form
ICH	International Conference on Harmonisation
IMP	Investigational Medicinal Product
ISF	Investigator Site File
JCI	Joint Commission International
LPLV	Last Patient Last Visit
MAH	Marketing Authorisation Holder
MP	Monitoring Plan
PI	Principal Investigator (Participating Site)
PRO	Patient Reported Outcome
SAE	Serious Adverse Event
SAP	Statistical Analysis Plan
SAR	Serious Adverse Reaction

SOP	Standard Operating Procedure
SmPC	Summary of Product Characteristics
SUSAR	Suspected Unexpected Serious Adverse Reaction
TMF	Trial Master File
GI	Gastro Intestinal
MMC	Migrating motor complex measurement
IGP	Intragastric pressure measurement
GLP-1	Glucagon-like peptide-1
GLP-2	Glucagon-like peptide-2
GIP	Gastric inhibitory polypeptide
FD	Functional dyspepsia
EPS	Epigastric pain syndrome
PDS	Postprandial distress syndrome
BA	Bile acids
FXR	Farnesoid X receptor
OCA	Obeticholic acid
PBC	Primary biliary cirrhosis
NASH	Non-alcoholic steatohepatitis
UDCA	Ursodeoxycholic acid
BMI	Body Mass Index

## FUNDING AND SUPPORT

Funder	Type of Financial or Non-Financial Support
Methusalem funding	Financial Support

Reasonable time investment and travel expenses incurred by Trial participants and directly related to participation in the Trial, will be reimbursed by the Sponsor, as follows:

- (i) At a flat rate of € 950  
When the subject does not complete the study, but terminates the study earlier, the compensation will be calculated as follow:
  - Stop at the end of visit 2: € 225
  - At the end of visit 4: € 575
  - At the end of visit 6: € 950
- (ii) If the subject require contraception to take part in this study, the subject will be reimbursed for the actual cost incurred.

A reimbursement payment log will be kept by the Investigator Site staff and made available for monitoring and verification purposes.

## ROLES AND RESPONSIBILITIES

The Principle Investigator (PI) is responsible for the conduct of the Trial at his/her Participating Site, and for protecting the rights, safety and well-being of the Trial participants. As such the PI must ensure adequate supervision of the Trial conduct at the Participating Site. If any tasks are delegated, the PI will maintain a log of appropriately qualified persons to whom he/she has delegated specified Trial-related duties. The PI will ensure that adequate training is provided and documented for all Trial staff, prior to conducting assigned Trial-related activities.

It is the Coordinating Investigator's (CI's) responsibility to supervise the general conduct (e.g. Trial progress, communication, protocol training and support of the participating sites, annual reporting to the Ethics Committee (EC), end of Trial notification(s) and results reporting...) of the Trial. The CI fulfils both Investigator and Sponsor responsibilities, as outlined in International Conference on Harmonisation – Good Clinical Practice (ICH-GCP) E6(R2) and applicable regulations.

PI and CI shall each be referred to as «Investigator(s)».

## TRIAL FLOWCHART

### Schedule of Events – Trial specific Procedures / Assessments

Please indicate in the flowchart with different colors whether a procedure is performed as part of the standard of care or specifically for the Trial.  
Describe the visits and applicable procedures/investigations (with a reference number or letter) in more detail in a footnote below the Trial flowchart

Procedures/ Assessment	Screening	Rando- misation	Treatment Period				
			Visit 0	Visit 1	Visit 2	Visit 3	Visit 4
Visits / Contacts			0	0	0	3	3
Timing (weeks)	-30 Days to -1	-30 Days to -1	day -7 to 0	day -7 to 0	day 17 to 21	day 17 to 21	day 66 to 70
Visit Window (days)							
Informed consent	X 						
Inclusion / Exclusion criteria	X						
Demographics	X						
Medical, Surgical history	X						
Physical examination	X						
Weight / Height	X						
Vital Signs	X						
Pregnancy Test	X						
Urinalysis							
Randomisation	X						
Study drug administration 				X	X	X	X
Migrating motor complex measurement 			X		X		X
Intragastric pressure measurement 			X		X		X
Blood collection 	X			X		X	X
Duodenal aspirates 	X			X		X	X
Patient Reported Outcomes (PRO) I (questionnaire) 							
Endoscopy 				X		X	X
Duodenal biopsy 				X		X	X
Diary				X		X	X
Stool specimens 				X		X	X
(Serious) Adverse event (S/AE) assessment				X		X	X
Concomitant Medication (CM)	X	X	X	X	X	X	X

1 Enrollment and screening questionnaires: the following questionnaires will be used for screening: Patient Health Questionnaire, Dutch version of Rome IV criteria questionnaire for functional GI disorders. Enrollment and screening will be done via an online system (Quatrics).

2 Study drug administration: assignment of treatment (placebo and obeticholic acid) will be randomized before study visit 1. Either placebo or obeticholic acid will be administered orally in a single-blind fashion for 21 days. After a washout period of 28 days, either placebo or obeticholic acid will be administered as appropriate for an additional 21 days.

4 Intragastric pressure measurement (IGP): Gastric accommodation will be assessed subsequently after MMC measurement. The drinking test will start from phase II of MMC. For the drinking test, nutrient drink (Nutridrink Nutricia 1.50 Kcal/100ml) will be taken orally at a constant speed of 60 ml/min. The maximum of liquid nutrient drink will be total 600ml. The subject will be asked to fill in a visual analogue scale for hunger and satiation and 6 epigastric symptoms (fullness, nausea, belching of air, cramps in the abdomen, bloating and pain) at 5-minute intervals. In addition, the subject also will have to score his/her satiation at 1-minute intervals by using a graphic rating scale that combines verbal descriptors on a scale graded from 0-5 (1, threshold; 5, maximum satiation). Blood samples will be taken every 10 min. Orally feeding will be stopped as soon as the subject reached the maximum score of 5 on their satiation scale or when they score maximally on one of the epigastric symptoms. In that case, the time of stop drinking will be recorded. One hour hereafter the catheters will be disconnected and removed.

5 Blood collection: During MMC measurement, blood samples (4ml per collection for motilin, octa-ghrelin) will be taken every 20 min within the first 60 min of MMC measurement, then every 10 min until the end of MMC phase III. If over 120 min, then blood samples will be collected every 20 min until the end of MMC measurement (maximum 300 min). During IGP measurement, blood samples (12 ml per collection for motilin, octa-ghrelin, GLP-1, GLP-2, GIP, insulin) will be collected every 10 min within the first 60 min. Plasma C4 will be evaluated at the first collected sample. A maximum amount of collected blood will be 150 ml.

6 Duodenal aspirates: Duodenal aspirates will be taken at around MMC phase III. Concentration of bile acids, including, glyco-cholic acid (GCA), tauro-cholic acid (TCA), glyco-cheno-deoxycholic acid (GCDDCA), and tauro-cheno-deoxycholic acid (TCDDCA), glyco-deoxycholic acid (GDDCA), tauro-deoxycholic acid (TDDCA), and tauro-ursodeoxycholic acid (TUDCA), for each participant will be measured with liquid chromatography-mass spectrometry (LC-MS) selected ion monitoring by the Pharmacotechnology and Biopharmacy group of [name] (KU Leuven) according to a previously published protocol (2). The pH of every duodenal fluid sample will be measured with pH-Meter 766 Calimaticon at room temperature.

7 Endoscopy: Endoscopy will be performed after a minimal fasting period of 8 hours. First, a sheathed and sealed biopsy forceps for aseptic mucosa sampling and outer diameter 1.8mm (MTW, Wesel, Germany) will be used for taking a maximum of 3 small biopsies (approximately 1 mm^2). Second, a single-use cytology brush will be used for superficial mucosal sampling. Finally, a Radial Jaw3 with needle forceps and outside diameter 2.2mm (Boston Scientific, Heredia, Costa Rica) will be used for 6 biopsies (approximately 2 mm^2) from the duodenum. All endoscopies will be performed by an experienced endoscopist. Before the procedure, local anesthetic xylocaine spray is applied in the throat with no sedation, unless demanded by subject in which case intravenous access is obtained before administration of IV Midazolam (maximum of 4mg). Aseptic biopsies (maximum 3) and brushings will be separately collected in sterile tubes, snap frozen in liquid nitrogen and stored at -80°C in the Laboratory of Molecular Bacteriology (Rega Institute) until microbial analysis. Of the conventional biopsies (n= 9 per subject per visit), 2 will be collected in RNAlater and stored at -80° in the Biobank until analysis of gene expression, 2 will be snap frozen in liquid nitrogen and stored at -80° in the Biobank until analysis of protein expression, 2 will be fixed in formalin or fixative with(-out) glutaraldehyde and stored at 4°C in the TARGID lab until later analysis of histology and 3 will be collected in ice-cold Hanks' Balanced Salt Solution (HBSS) buffer and analyzed immediately in the TARGID lab for permeability.

8 Stool samples will be collected before administration of placebo or obeticholic acid (day 0 for intervention 1, day 28 for intervention 2), after administration (day 2, 4, 7, 14, 21 for intervention 1, day 30, 32, 35, 42, 49 for intervention 2). Samples are temporarily stored by the participants in their home freezer. Within 2 weeks, samples will be brought back to UZ Leuven.

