## 5.3 Concomitant / Prohibited Medication / Treatment

The following drugs must not be used 2 weeks before, during and 1 week after the study

- Drugs that can affect gastrointestinal function, motility or sensitivity or gastric acidity.
- Centrally acting medication, including antidepressants, antipsychotics and/or benzodiazepines
- Warfarin
- Proton pump inhibitors

If these drugs are taken during study medication, IMP medication will be discontinued and the subject will be excluded from the study at that time. Study data up to the time of exclusion will be available.

If these drugs are taken during the washout period, a period of at least 2 weeks should be allowed before starting the second medication.

The following drugs must not be used 1 year before, during and 1 week after the study

- Centrally acting medication, including antidepressants, antipsychotics and/or benzodiazepines (in the last year before screening visit).

If these drugs are taken during study medication, IMP medication will be discontinued and the subject will be excluded from the study at that time. Study data up to the time of exclusion will be available.

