## 7.1 Sample Size Determination

Twelve healthy volunteers will be enrolled in this placebo-controlled cross-over study. The number of volunteers to be included is calculated with a two-tailed t-test comparing two dependent means. Power calculations were based on previous results on the effect of cholestyramine (a bile acid sequestrant) on hunger sensation in healthy volunteers (23). We assume a similar effect of obeticholic acid on hunger sensation and a similar within-participant variability. We specified the following parameters: an error probability of 5%, effect size of 1.0 and a power of 80%. Based on these parameters we need to include 10 volunteers in order to highlight the expected differences. Twelve volunteers will be included to anticipate a potential dropout. Power calculations were performed with GPower version 3.0.10.

Approximately 15 participants will be screened to achieve 6 randomly assigned to Trial treatment and 6 evaluable participants for an estimated total of 12 evaluable participants per treatment group.

A maximum of 12 participants will be randomly assigned to Trial treatment such that approximately 10 evaluable participants complete the Trial.

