## 7.2 Statistical Analysis

Data from all subjects who completed the study will be included for analysis. Statistical analysis of the different parameters will be performed in SPSS for Windows (SPSS Inc., Chicago, IL, USA). Curves of whole blood glucose, plasma levels of motilin and ghrelin GLP-1, GLP-2, GIP and insulin and hunger / appetite scores over time will be analyzed using the mixed models procedure, taking into account the course of the curves over different time points. Gastric motility and BA composition will be compared with Two-tailed paired t tests or Wilcoxon signed-rank tests, depending on data distribution. Non-parametric test were applied to analyse microbiome data, with multiple testing correction whenever applicable (adjustment for false discovery rate (FDR)). Data obtained from endoscopy and gastric motility measurements prior to the start of treatment in the first part of the crossover study will be used as pre-treatment data in the second part. Results will be found significant at  $p<0.05$  significance level.

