## 8 Data handling

Data handling and data flows for the Trial are summarized below and will be described in more detail in the Trial-specific Data Management Plan (DMP).

Data for this study will be captured via electronic CRFs (open clinica) with pseudonymisation. Time and date of entry, changes made and reasons for change will be recorded. Complete information for each patient visit, status, procedure, and test will be appropriately recorded. For dose administration, the date and exact time will be captured. For each patient randomized and treated, an eCRF must be completed. If a participant withdraws from the study, the reason must be noted on the eCRF. The Investigator will ensure the accuracy, completeness, and timeliness of the data reported in the eCRF. The participant's name or other identifiers will be stored separately from the Trial data and replaced with a unique code to create a new identity for the participant, for the purpose of the Trial. In such case data are encoded and solely the Investigator and his/her Trial staff shall be able to link the data to an identifiable person. The code list must be retained on site, in a secured place with restricted access and can under no circumstances leave the site or be accessed by unauthorized persons.

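### Footnote 8 puts the second-period stool samples on days 28 to 49, but footnote 2 and the visit windows start period 2 at about day 49

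*Combined protocol and SAP*

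**What the plan says.** The dosing timetable is in footnote 2 of the Trial Flowchart. The first treatment lasts 21 days, and then: "After a washout period of 28 days, either placebo or obeticholic acid will be administered as appropriate for an additional 21 days". The visit window row places the end-of-period assessments at day 17 to 21 and day 66 to 70.

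The stool timetable is in footnote 8. A sample is taken "before administration of placebo or obeticholic acid (day 0 for intervention 1, day 28 for intervention 2". The post-dose samples follow on days 2, 4, 7, 14 and 21 in the first intervention and on "day 30, 32, 35, 42, 49 for intervention 2". One sentence lists both interventions and does not mention a change of day origin. Participants freeze the samples at home and bring them in later.

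Three other places bear on the point:

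- Section 5.3 allows period 2 to start late: "If these drugs are taken during the washout period, a period of at least 2 weeks should be allowed before starting the second medication".
- Section 8 records dosing times: "For dose administration, the date and exact time will be captured".
- Section 7.2 describes the microbiome analysis only in general terms: "Non-parametric test were applied to analyse microbiome data, with multiple testing correction whenever applicable". It does not say how the repeated stools of one participant are combined.

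**The concern.** The stool list moves by 28 days between interventions, while the dosing schedule and the visit windows move by 49. If the listed days are followed on the flowchart clock, samples labelled as post-dose in period 2 are collected in the washout. For a participant who receives placebo first, stools labelled as obeticholic acid would be drug-free. For one who receives obeticholic acid first, the period-2 pre-dose stool would come about a week after the last active tablet.

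Gut microbiota is the third secondary objective in the Trial Synopsis, and stool is one of its specimen types. Mislabelled samples would bias the within-participant comparison of treatments. Because dose dates and times are captured, mistimed stools could be recognised afterwards if stool dates are recorded too. Stools that should have been taken on treatment and were not could not be recovered. Collection takes place at home, so a participant given a bare day number may have no staff present to question it.

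The primary endpoint (appetite and hunger) and the duodenal microbiota samples do not depend on footnote 8.

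**Working it through.** **Inputs.** Treatment 21 days, washout 28 days, treatment 21 days (footnote 2). End-of-period windows day 17 to 21 and day 66 to 70 (flowchart). Stool days 0, 2, 4, 7, 14, 21 and 28, 30, 32, 35, 42, 49 (footnote 8). Twelve randomised and about 10 completers (section 7.1).

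**1. Reproduce the plan's own window.** Start of period 2 = 21 + 28 = day 49. Adding the period-1 window gives 49 + 17 = 66 and 49 + 21 = 70, which is exactly the printed day 66 to 70. Footnote 2 and the windows agree.

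**2. Shift in the stool list.** 28 − 0, 30 − 2, 32 − 4, 35 − 7, 42 − 14 and 49 − 21 are all 28. On the flowchart clock this would imply a washout of 28 − 21 = 7 days, which footnote 2 contradicts.

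**3. Position of each stool relative to the first period-2 dose, on the flowchart clock.** The protocol does not say whether the first tablet falls on day 0 or day 1, so both are shown. With day 0, doses run from day 0 to 20, washout from 21 to 48, and period 2 starts on day 49. With day 1, doses run from day 1 to 21, washout from 22 to 49, and period 2 starts on day 50.

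| Listed day | Label | Minus 49 | Minus 50 |
|---|---|---|---|
| 28 | pre-dose | −21 | −22 |
| 30 | post-dose | −19 | −20 |
| 32 | post-dose | −17 | −18 |
| 35 | post-dose | −14 | −15 |
| 42 | post-dose | −7 | −8 |
| 49 | post-dose | 0 | −1 |

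Four of the five post-dose stools precede dosing in the first case, and the fifth falls on the first dosing day. In the second case all five precede dosing. The pre-dose stool comes 28 − 20 = 8 or 28 − 21 = 7 days after the last period-1 dose.

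**4. Counts.** Each participant gives 5 + 5 = 10 post-dose stools.

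- 12 participants: 4 × 12 = 48 to 5 × 12 = 60, of 10 × 12 = 120.
- 10 completers: 4 × 10 = 40 to 5 × 10 = 50, of 10 × 10 = 100.

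**5. Counting from the end of period 1.** Adding 21 to each listed day gives 49, 51, 53, 56, 63 and 70. These equal the period-1 days plus 49, and day 70 lies inside the last visit window. Of all origins from day 0 to day 49, only day 21 gives this match. On this count no post-dose stool is mistimed, provided period 2 starts on schedule.

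**6. A late start under section 5.3.** Assume a single intake of a prohibited drug d days after the end of period 1, with the two weeks counted from that intake. The earliest start is then max(28, d + 14). For d = 15 to 28 this gives days 29 to 42 on the end-of-period-1 count. With a start on day 42, the stools on days 30, 32 and 35 precede dosing and day 42 is the first dosing day. Up to three of the five post-dose stools in that participant would be mistimed, even with the origin stated.

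**The case against.** The strongest reply is that this is an unlabelled day origin and not a conflicting schedule. Footnote 8 ties its days to before and after administration, 28 is exactly the washout length, and all six days fit when counted from the end of period 1. Staff would have to collect post-dose stools before any period-2 tablet had been taken, against the footnote's own wording. This stands as an argument about likelihood: the literal reading is probably not the intended one. It does not remove the contradiction, because the same sentence counts intervention 1 from the start of treatment and nothing announces a restart.

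A second reply is that the loss would be partial. The period-1 series is complete whichever clock is used, and the flowchart marks a stool at day 66 to 70, so an end-of-period-2 sample may survive. This also stands, with a caveat: the flowchart columns are damaged in the text available, and since stools are stored at home the mark could mean hand-over and not sampling. What is clearly at risk is the earlier part of the period-2 time course. The arithmetic does not depend on the flowchart, because footnote 2 alone gives day 49.

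A third reply is that the late-start case needs a particular and perhaps rare event. That is fair. It matters only for the form of the correction: stating the origin would not be enough in such a participant.

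Finally, neither the size nor the direction of any bias can be given, and stool is one of several specimen types under a secondary objective. That limits the weight of the point, and the fix asked for is correspondingly small.

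**Conclusion.** The concern holds. Footnote 8 contradicts footnote 2 and the visit windows on the only clock that the protocol states: a shift of 28 days against 49. Followed that way, 4 or 5 of each participant's 10 post-dose stools precede period-2 dosing (48 to 60 of 120 with 12 participants, 40 to 50 of 100 with 10 completers), and the period-2 pre-dose stool is 21 to 22 days early. The range reflects only whether the first tablet falls on day 0 or day 1.

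Counted from the end of period 1, the number is none, apart from a participant whose second period starts late; under the assumptions in step 6, up to three stools would be affected in that participant.

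Confidence in the contradiction is high. Confidence that the days would be followed literally is low to moderate. The consequence is confined to the stool part of the third secondary objective. It should be corrected, because the correction is cheap and missed on-treatment samples cannot be collected afterwards.

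**What to change.** Reconcile footnote 8 with footnote 2 and the visit windows. This review takes no position on the length of the washout or on the delay in section 5.3.

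- Give the stool days relative to the first dose of each period, using footnote 8's own offsets: pre-dose, then +2, +4, +7, +14 and +21 days. They then stay correct if period 2 starts late.
- Say whether the first tablet counts as day 0 or day 1, in the same way for both periods.
- Confirm that the stool marked at day 66 to 70 is the +21-day sample.
- Align any participant instructions that give calendar days, and record the date of each stool so that it can be checked against the recorded dose times.

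The cost is a one-line protocol clarification and a check of the participant instructions. No samples or visits are added.

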## I Background, Rationale and Risk Assessment

Functional dyspepsia (FD) is a common functional gastroduodenal disorder that has a great social and economic impact in patients. It is subdivided in two groups depending on the symptom pattern. Epigastric pain syndrome (EPS) is characterized by meal-unrelated symptoms such as epigastric pain and epigastric burning; and postprandial distress syndrome (PDS) characterize by meal-related symptoms such as postprandial fullness and early satiation (1). The pathophysiology of FD remains poorly understood and is most likely heterogeneous, but likely candidates are genetic factors, stress and duodenal luminal factors, including bile acids (BA) (2).

